Thalidomide is another immunomodulatory agent used to treat the cutaneous activity of SLE and LEC, even in patients refractory to other medications (Knop et al., 1983; Kyriakis et al., 2000; Coelho et al., 2005; Cuadrado et al., 2005). Its high efficacy associated with a very rapid response of the cutaneous picture, made this drug one of the first choices in patients without contraindication. Cuadrado et al. demonstrated in a retrospective study with 48 patients with SLE and skin lesions refractory to treatment with antimalarials, prednisone, azathioprine, cyclosporine and cyclophosphamide a high partial or complete clinical response rate (81%) with doses of 25, 50 or 100 mg/day of thalidomide (Cuadrado et al., 2005). Thus, thalidomide is very useful as an agent inducing remission of skin activity of SLE (Cuadrado et al., 2005). In this study, the treatment time was around one year. Thrombotic events were not observed, although some patients had positive antiphospholipid antibodies. The most common adverse effects were dizziness, abdominal pain, and peripheral polyneuropathy. Peripheral polyneuropathy occurred in 27% of patients, including 18.8% with neurological symptoms and alterations in ENMG, 4.2% only with findings at ENMG and 4.2% with neurological symptoms despite normal MGS. Regarding the time of disease, this effect seems to occur around 14 months of treatment (Briani et al., 2004).

In Brazil, thalidomide is indicated for use in SLE, subacute cutaneous LE and discoid LE (Ministry of Health, 2013). However, due to its known teratogenicity when used during pregnancy, it is recommended for male patients (who agree to use condoms throughout the treatment period and up to 30 days after the end of the same, even if they have already undergone vasectomy, as its possible excretion in the seminal fluid is not known) and to women without fertility potential (i.e., who have been in the postmenopausal phase for at least one year, or who have undergone tubal ligation or hysterectomy) and who agree to use it according to the Term of Responsibility/Clarification (Ministry of Health, 2013; System for Thalidomide Education and Prescribing Safety, Zeldis et al., 1999).

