- The possible combination of plasma levels of TNF-, α IFN-1, BAFF (B-cell activator factor) and thalidomide levels in the blood and saliva with the therapeutic response and the adverse effects.

Secondary:

- Evaluate the possible association between TNF-levels, adjoin molecules, apoptosis markers and growth factors in skin biopsy samples with efficacy and adverse effects.

- Evaluate the presence of fine fiber neuropathy in skin biopsy specimens.

- Establishment of a pharmacokinetic-pharmacodynamic model of thalidomide dose reduction in patients with SLE.

NUMBER OF INDIVIDUALS

40 patients with lupus (SLE) and active cutaneous involvement will be included.

STUDY DESIGN

A prospective study for a period of 12 months with adult patients with SLE (according to the classification criteria of the American College of Rheumatology- ACR) (Hochberg, 1997) with active skin lesions at the entrance regardless the use of hydroxychloroquine and/or dapsone and/or prednisone and/or immunosuppressants, and who are eligible for the use of thalidomide (see inclusion criteria) (Ministry of Health, 2013; System for Thalidomide Education and Prescribing Safety, Zeldis et al., 1999).

The initial dose of thalidomide will be 100 mg/day for 3 months and reduced to 50 mg/day and 25 mg/day, at any time depending on the therapeutic response until complete 12 months of treatment.

All patients will be treated simultaneously with hydroxychloroquine, unless there is contraindication for use of this medication.

The other drugs used for SLE control will be maintained during the study, including prednisone (with subsequent gradual dose decrease in case of improvement of skin lesions).

Patients will be clinically evaluated at baseline, then 1 month, 6 months and 12 months after inclusion for:

- the global activity of the disease through the SLEDAI-2K (Systemic Lupus Erythematosus Disease Activity Index 2000) (Gladman et al., 2002);

- the index of activity and skin severity (CLASI) (Albrecht et al., 2005);

- possible adverse effects and adherence by the Medication Adherence Self-report Inventory (MASRI) applied by a pharmacist not directly involved in patient care (Koneru et al., 2007);

- quality of life by the visual analog scale and the SF36 questionnaire (Mosca et al., 2010).

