In addition, we hope to determine whether the mechanism of thalidomide-induced neuropathy would target thin nerve fiber injury to histological skin analysis of patients treated with this medication.

SAMPLE SIZE

This is a convenience sample.

STATISTICAL PLAN

Patients with vs. without therapeutic response to thalidomide and vs. without signs of peripheral polyneuropathy will be compared for categorical variables by fisher's exact or chi-square test and, as for

quantitative variables, by t-Student or Mann-Whitney tests, when applicable. The influence of the different variables on disease activity and polyneuropathy will be evaluated by multivariate analysis.

References

- Ackerman, AB. Histologic diagnosis of inflammatory skin diseases. Philadelphia, Lea & Febiger, 1978. P. 813.
- Agency for Healthcare Research and Quality. Priority Areas for National Action: Transforming Health Care Quality. Rockville, MD: Agency for Healthcare Research and Quality; 2003.
- Bernstein HN. Ocular safety of hydroxychloroquine. *Ann Ophthalmol.* 1991;23(8):292-6.

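### Project 2 tests its marker-response objective by comparing responders with non-responders, response being undefined; 1-month CLASI as a score would use the same patients about twice as efficiently

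*Combined protocol and SAP*

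**What the plan says.** All references are to Project 2 of the combined protocol and SAP.

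- **Objectives.** The primary objective relates TNF-alpha, IFN-1, BAFF and "thalidomide levels in the blood and saliva with the therapeutic response and the adverse effects". Counting blood and saliva separately, that is five markers.
- **Number of individuals; Sample size.** "40 patients with lupus (SLE) and active cutaneous involvement will be included", and "This is a convenience sample". No alpha, power, effect size or allowance for losses is given.
- **Statistical plan.** "Patients with vs. without therapeutic response to thalidomide and vs. without signs of peripheral polyneuropathy will be compared for categorical variables" by Fisher or chi-square tests, and for quantitative variables by t or Mann-Whitney tests. It then adds: "The influence of the different variables on disease activity and polyneuropathy will be evaluated by multivariate analysis". Model type, outcome scale and covariates are not stated.
- **Study design.** SLEDAI-2K and CLASI are listed for all patients at baseline and at 1, 6 and 12 months. Cytokines and thalidomide are sampled at time zero, 30 days and 3, 6, 9 and 12 months. Change in CLASI is named as an outcome only for the pharmacokinetic-pharmacodynamic part (two groups of 5, days 0 and 30).
- **Safety.** A patient without clinical response within 2 months, or with suspected neuropathy at any time, stops thalidomide and leaves the study.
- **Justification.** The only response rate in the documents is "a high partial or complete clinical response rate (81%) with doses of 25, 50 or 100 mg/day of thalidomide", from a "retrospective study with 48 patients with SLE and skin lesions refractory to treatment". The same source gives polyneuropathy in 27%.

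No section defines therapeutic response or gives a CLASI cut-off.

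**The concern.** Each marker is a quantity, and so is CLASI. The only stated test of a marker against the primary objective nevertheless replaces the outcome with a yes/no group. Three things follow.

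- A yes/no version of a graded outcome carries less information, and the loss grows as the split becomes uneven. A high response rate makes an uneven split likely.
- With response undefined, the cut-off can be settled after the data are seen.
- The sample is a fixed convenience sample, so the choice of analysis is the main lever on power.

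At stake is the primary question: a real relation between a marker and skin response could well be missed. The polyneuropathy model has a separate problem. It has few events for the number of candidate predictors, so its estimates could be unstable.

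**Working it through.** Project 2 states no power calculation, so there is no figure to reproduce. Alpha is taken as two-sided 0.05 and target power as 80%; both are assumptions.

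**Step 1, the likely split.** Inputs: N = 40 (Number of individuals) and 81% response (Justification).
- Responders 40 × 0.81 = 32.4; non-responders 40 × 0.19 = 7.6; about 32 v 8.
- The source had 48 patients, and 0.81 × 48 = 38.9, so about 39 of 48. The exact 95% interval is 67% to 91%.
- Non-responders then range from 40 × 0.09 = 3.6 to 40 × 0.33 = 13.2, about 4 to 13.

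**Step 2, information kept.** For a normal outcome cut at proportion p, relative efficiency is φ(z_p)² / [p(1 − p)], where φ is the standard normal density.

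| Response rate | Efficiency | Information lost |
|---|---|---|
| 50% (best case) | 0.637 | 36% |
| 67% | 0.593 | 41% |
| 81% | 0.271² / (0.81 × 0.19) = 0.478 | 52% |
| 91% | 0.322 | 68% |

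At 81%, 40 patients act like 40 × 0.478 = 19.

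**Step 3, power.** With 40 patients and the continuous score, the Fisher z approximation gives 80% power at r = tanh[(1.960 + 0.842)/√37] = 0.43. The documents give no marker effect, so this r is illustrative. In 20,000 simulated trials of 40, the lowest 8 outcomes were called non-responders:

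| True r | Continuous score | t test, 32 v 8 | Mann-Whitney, 32 v 8 |
|---|---|---|---|
| 0.43 | 81% | 47% | 44% |
| 0.50 | 93% | 61% | 58% |
| 0.60 | 99% | 80% | 78% |

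For 80% power the 32 v 8 comparison needs a marker difference of (1.960 + 0.842) × √(1/32 + 1/8) = 1.11 SD, or 1.14 SD with the t distribution.

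**Step 4, which visit can be used.** Under the Safety rule, non-responders have no planned CLASI at 6 or 12 months. Take r = 0.43 and remove the 8 lowest responders. A regression on the remaining 32 has about 51% power, little better than the t test. If a further 27% are lost to neuropathy (assumed at random), it falls to about 38%. The sample is also selected on the outcome. The 1-month visit comes before the 2-month point, and CLASI and the marker samples are both scheduled then.

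**Step 5, the multivariable models.** Polyneuropathy: 40 × 0.27 = 10.8, about 11 events, or 11/5 = 2.2 per marker with five markers. Disease activity: if SLEDAI-2K or CLASI is modelled as a score, all patients with a score contribute and the number of non-responders is not the limit.

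**The case against.** Five points can be made for the plan.

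- **The multivariable analysis may already use the score.** It is planned for disease activity and polyneuropathy, and Study design measures activity with two graded indices. A reader might infer that about 8 non-responders leave too few for any multivariable model. The documents do not support that, because no model of binary response is planned. What stands is that outcome, scale and covariates are unstated.
- **CLASI is not secure at every visit.** A reader might take it as available in everyone throughout follow-up. The 2-month rule contradicts that, and a regression on 6- or 12-month scores would give up most of the gain in power and introduce selection. This limits the remedy to the 1-month score; it does not remove the concern.
- **Response is a real state in this design.** It decides who continues, and it is nowhere said to be a CLASI cut-off. That is fair. The efficiency figures hold only so far as response is in effect a threshold on a roughly normal CLASI change.
- **The 32 v 8 split is a projection.** It comes from a cited retrospective study that counted partial responses over a range of doses. It is not a planning assumption. Even so, the loss is at least 36% at any split.
- **This is an uncontrolled convenience sample with no stated power.** That lowers what can be claimed, but it does not favour the less efficient test when the score is already scheduled.

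**Conclusion.** The concern holds for the marker-response test. The stated two-group comparison rests on an undefined response. It is expected to discard about half the information in a CLASI score that is scheduled for every patient at baseline and 1 month: 52% at 81% response, 41% to 68% over the interval of the cited rate, and never less than 36%. In the illustration at r = 0.43, power falls from about 81% to 47% or 44%. These sizes assume that response acts as a cut of a roughly normal CLASI change and that all 40 patients have a 1-month score.

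Of the planned multivariable models, only the polyneuropathy model is shown to be thin, at about 11 events or about 2 per marker. The disease-activity model is under-specified. It is not shown to be unworkable.

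**What to change.** 1. Make the main test of each marker a regression of 1-month CLASI on the marker (baseline or 30-day level, named in advance), with baseline CLASI as covariate. Use a rank-based version if the score is skewed. Include all patients with a 1-month score.
2. Use 6- and 12-month CLASI only in a supportive analysis that accounts for outcome-dependent withdrawal, for example a mixed model using all scores up to withdrawal. Do not use a complete-case regression.
3. Define response before analysis and keep the responder v non-responder comparison as secondary.
4. State that the multivariable disease-activity model uses the graded score, and name the index, visit and covariates.
5. Limit the polyneuropathy model to one or two pre-named predictors with a Firth fit, and label further models exploratory.

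No extra visits or samples are needed. The cost is wording in the Statistical plan, including how withdrawal is handled. The downsides are that the familiar responder comparison becomes secondary and that the main test reflects early, 1-month response.

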Plasma levels of TNF-, IFN-1, BAFF, transforming growth factor-beta (TGF- β) and thalidomide levels in the blood and saliva will be performed at zero time, at 30 days, 3 months, 6 months, 9 months and 12 months.

The clinical evaluation of peripheral neuropathy will be performed at each consultation by anamnesis and through THE ENMG at baseline, at 6 months and at 12 months.

Skin biopsy of an active lesion will be performed at baseline for histological evaluation, including the study of immunohistochemistry expression of TNF-, TGF $\alpha\beta$ (Kuhn et al., 2010; Yu et al., 2013) and plasmacytoid and pro-apoptotic dendritic cell markers such as caspase 3, CD25, CD35, CD21, CD36, CD68, CD31, detection of IgG, IgM, C3 and T and B cell markers (Bălănescu et al., 2010).

Skin biopsies of uninjured skin will be obtained from the thigh area, at baseline and at 6 months for the fine fiber neuropathy assessment through immunostaining with PGP 9.5 (Birnbau & Bingham, 2014).

- Pharmacokinetic-pharmacodynamic model of use of thalidomide will be performed in two groups of 5 patients with different doses (50 mg/day and 100 mg/day).

Outcomes: evaluations on days 0 and 30.

a) Improvement in skin symptoms and severity scores [(Cutaneous Lupus Area and Severity Activity Index score (CLASI)]. Change in CLASI score assessing the activity/severity criteria from 0 to 70 will be performed. The reduction represents an improvement in skin injury related to lupus in terms of activity and/or severity. CLASI evaluates erythema and scar/hypertrophy/atrophy in 13 anatomical areas. Membrane lesions and alopecia are also part of this index.

b) Cytokine dosage. Plasma levels of TNF- α and IFN-1 will be determined by Luminex MAP (EMD Millipore Corporation®). Plasma samples will be stored at -80oC until use.

TARGET POPULATION

Inclusion criteria:

- Adult patients with SLE (according to the classification criteria of the American College of Rheumatology) (Hochberg, 1997) with active skin lesions at the entrance to the research despite the use of hydroxychloroquine and/or prednisone and/or immunosuppressants who are eligible for thalidomide use.

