Histological sections submitted to immunohistochemistry techniques to demonstrate cellular and cytokine elements will be digitized by the Panoramic Scan (3D Histech, Hungary) scanner to obtain virtual histological slides. The reading of the material and capture of the images to be analyzed will be carried out with the program Panoramic Viewer version 1.15.2.21080 (3D Histech, Budapest, Hungary). The quantification of immune tagged cellular elements will be performed with the aid of image analysis program Image Pro Plus version 4.5.0.29 (MediaCybernetics Inc. , Rockville, MD, USA).

The quantification of fine nerve fibers will be performed by counting intraepidermal nerve fibers per millimeter of dermal epidermal junction and the relationship between area of marked subepidermal nerve fibers and total area of papillary dermis examined (Rodrigues Júnior, 2011).

Safety

Patients who fit the safety recommendations of the Ministry of Health will be included.

Clinical (with special attention to symptoms of peripheral polyneuropathy) and laboratory of adverse effects (including leukocyte count) will be performed at the entrance into the study and each medical consultation.

The ENMG will be performed to include in the study, at 6 months and at the end of the study.

If there is no clinical response within 2 months of the use of thalidomide, or in the clinical suspicion or enmg of peripheral neuropathy at any time, thalidomide will be suspended (out of the study) and follow-up of the patient will be continued in the outpatient clinics of the Rheumatology and Dermatology Services of HC-FMUSP.

WITHDRAWALS

See item Security.

ORIGINALITY WITH CARE IMPACT

There are no studies correlating tissue expression of cytokines with blood and salivary levels of thalidomide and its possible role as a predictor of response and adverse effects in patients in skin lesions of SLE. In addition, there are no studies on the value of skin biopsy in the diagnosis of thalidomide-induced neuropathy.

The expected impact with the availability of blood and salivary dosage of thalidomide in clinical practice is that this parameter may be a predictor of clinical response and neuropathy.

ADVANCES IN MECHANISM

The expected advance is a better understanding of the role of thalidomide in the expression of cytokines in the cutaneous lesion of SLE.

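### Project 2 compares patients with and without polyneuropathy with no account of time on thalidomide, although non-responders leave at about 2 months, so a marker of non-response can look protective against neuropathy

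*Combined protocol and SAP*

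**What the plan says.** Project 2 is described as "A prospective study for a period of 12 months with adult patients with SLE". On numbers it says "40 patients with lupus (SLE) and active cutaneous involvement will be included", and under Sample Size "This is a convenience sample". The primary objective relates plasma cytokines and thalidomide levels both to therapeutic response and to adverse effects.

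The Statistical Plan covers both outcomes in one sentence: "Patients with vs. without therapeutic response to thalidomide and vs. without signs of peripheral polyneuropathy will be compared". The tests are Fisher or chi-square for categorical variables and t or Mann-Whitney for quantitative ones. An unspecified multivariate analysis of disease activity and polyneuropathy follows. No analysis set, exposure time, censoring rule or time-to-event method is named.

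Three other places bear on this:

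- Safety: "If there is no clinical response within 2 months of the use of thalidomide", or if neuropathy is suspected clinically or on ENMG at any time, "thalidomide will be suspended (out of the study) and follow-up of the patient will be continued in the outpatient clinics".
- Study Design: neuropathy is assessed by history at each consultation and "through THE ENMG at baseline, at 6 months and at 12 months". Uninjured-skin biopsies for small-fibre neuropathy are taken at baseline and 6 months.
- Justification: of peripheral polyneuropathy, "this effect seems to occur around 14 months of treatment".

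**The concern.** A patient who does not respond stops the drug at about 2 months and leaves with no scheduled nerve test after baseline. Stopping for non-response ends exposure to the toxic agent. If that patient is then counted as without neuropathy, the comparison group mixes people who tolerated long treatment with people who were hardly exposed.

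The result is a bias with a known direction. A marker that differs in non-responders (a cytokine, or a low drug level) is over-represented among patients without neuropathy, even if it has nothing to do with nerve damage. The project hopes that blood and salivary thalidomide will predict both response and neuropathy. If low drug levels go with non-response, the design alone can produce an apparent link between low levels and freedom from neuropathy.

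**Working it through.** The sample size of 40 is a convenience figure with no calculation behind it, so there is nothing to reproduce. The check is how many patients could be misplaced and what that does to the test.

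**Inputs from the documents** (Project 2 Justification, unless stated)

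- N = 40, follow-up 12 months (Number of Individuals, Study Design).
- Response 81% in a retrospective series of 48 patients treated for around one year.
- Polyneuropathy 27% in that series. The components agree: 18.8 + 4.2 + 4.2 = 27.2%.

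**Assumptions**

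- 2-month non-response of 100 − 81 = 19%. The documents give no 2-month rate, so 10% to 40% is also shown.
- 27% neuropathy among patients who stay on drug.
- Early leavers are counted as without neuropathy unless they show signs.

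**Step 1: share of the group without neuropathy, if no leaver shows signs**

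- Early leavers: 40 × 0.19 = 7.6.
- Cases: 0.27 × 32.4 = 8.75.
- Without neuropathy: 40 − 8.75 = 31.25.
- Share who are early leavers: 7.6 / 31.25 = 24.3%.
- At 10% non-response: 4 / (40 − 0.27 × 36) = 4 / 30.28 = 13%.
- At 40%: 16 / (40 − 0.27 × 24) = 16 / 33.52 = 48%.

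**Step 2: allowing for early signs**

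- With a constant hazard, 2-month risk is 1 − 0.73^(2/12) = 5.1%.
- Cases: 8.75 + 7.6 × 0.051 = 9.1.
- Early leavers without signs: 7.6 × 0.949 = 7.2. Share: 7.2 / 30.9 = 23%.
- If onset is late, as the 14-month figure suggests, the 2-month risk is lower and the share moves back towards 24%.

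**Step 3: effect on a marker unrelated to neuropathy**

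- Assume the marker differs by 1 SD in non-responders. The false group difference is 0.243 × 1 SD = 0.24 SD.
- SE of the standardised difference: √(1/8.75 + 1/31.25) = 0.38. Ratio: 0.243 / 0.382 = 0.64 SE.
- Simulated rejection by a 5% t-test with no early signs: 8.0% at 19% non-response and 11.3% at 30%.
- Simulated rejection by Mann-Whitney with the 5.1% early risk: 6.5% at 19% and 10% at 40%. With a 1.5 SD shift: 8.2% and 17%.
- For a binary marker assumed present in 70% of non-responders and 30% of responders, with true odds ratio 1, the apparent odds ratio is 0.72 with the 5.1% early risk, or 0.65 if no early signs are seen.

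**Step 4: the same comparison among patients still on drug**

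Simulated rejection returns to 5.1% and 5.3% for the t-test (19% and 30% non-response) and to 4.0-5.0% for Mann-Whitney. The apparent odds ratio returns to 1.00. These simulations contain no dose reduction.

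**The case against.** The strongest reply is that the plan never says how early leavers are classified. If they are left out of the neuropathy comparison, this bias does not arise. That is correct: the scoring is inferred. But one sentence defines both splits, the response comparison needs the non-responders in the dataset, and no separate set is named for neuropathy. Inclusion is therefore the natural reading. Exclusion would also have to be written down, because the results would then describe only patients who continue past 2 months.

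A reader might go further and infer any of the following. The documents do not support them.

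- *Early leavers can only be counted as without neuropathy.* Neuropathy is sought by history at every consultation, and clinical suspicion alone triggers action, so a leaver with early signs could be a case.
- *About 19% of patients will leave at 2 months.* The 81% comes from a retrospective series treated for around a year at 25, 50 or 100 mg/day. It is not a 2-month rate.
- *The neuropathy rate will read 21.9% instead of 27%.* The 27% describes the whole cited series, non-responders included. If they contributed no cases, the rate among the others would be 27 / 0.81 = 33%, and the whole-cohort rate would still be 27%. No dilution can be claimed. Using 33% in step 1 gives 10.8 cases and a share of 7.6 / 29.2 = 26%, so the main finding hardly moves.
- *The multivariate model has the same fault.* No covariates are named, so this cannot be said.

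Two further points stand. The rise in false positives is modest and rests on an assumed marker shift. And if onset is typically around 14 months, many patients who complete 12 months will also finish before it. That lowers the expected number of cases, but it does not put early leavers on an equal footing with completers.

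**Conclusion.** The point holds in a conditional form. The timing is documented: non-responders stop at about 2 months, the next scheduled nerve tests are at 6 months, and the planned tests ignore time on drug. That early leavers count as without neuropathy is the natural reading, not a stated rule. On that reading, a marker of non-response is biased towards looking protective.

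The size is moderate. About 8 of 40 patients are affected if non-response is near 19%, or roughly 23-24% of the group without neuropathy (13% to 48% for non-response of 10% to 40%). With an assumed 1 SD marker shift, a 5% test rejects about 6.5% to 8% of the time at 19% non-response, and more at higher rates. No claim is made about the neuropathy rate itself. The plan should be changed because the direction of the bias is predictable, it bears on the adverse-effect half of the primary objective, and the remedy is inexpensive.

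**What to change.** In the Project 2 Statistical Plan, for the neuropathy comparison only:

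- Define time at risk as running from first thalidomide dose to first neuropathy sign or stop of thalidomide, and censor at drug stop.
- Relate each marker to neuropathy one at a time by log-rank or Cox regression. With about 9 expected cases, a model with several markers is not supportable. Alternatively, compare each case with patients still on drug at the same month, which suits ENMG performed only at 6 and 12 months.
- If the two-group tests are kept, apply the same still-on-drug landmark to both groups, not just to those without neuropathy. State that the results apply to patients who continue past 2 months.

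The response comparison keeps all patients, and no clinical rule changes.

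The cost is a change of wording plus recording of thalidomide start and stop dates, which the documents do not say are collected. The landmark version loses about 8 comparison patients (32.4 − 8.75 = about 24 instead of 31) and any case that arises before the landmark. One problem remains: the dose is reduced according to response among patients still treated, so exposure still depends on response after 2 months. This should be stated as a limitation.
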